#### Follow up procedures:

Following right heart catheterization and lidocaine splanchnic nerve block the will be observed for monitored in the cath lab holding area for 3 hours following nerve block (SOC).

- Continuous recording of urine output for the procedure day (CS) will be achieved by recording urine output at the beginning of pre-testing, just before the cath lab procedure, just after the cath lab procedure and before the subject leaves home.
- Basic vitals (SOC) and orthostatic vitals (CS) following the cath lab procedure and record heart rate variability using a non-invasive wrist monitor (CS).
- Repeat labs after the procedure before the subject leaves. Pro-BNP, BMP, serum sodium (all CS)
- Labs: Angiotensin 2, plasma metanephrines (if on inotropes), plasma catecholamines, vasopressin, lactate, and urine sodium will be collected immediately before and after the procedure
- Dyspnea questionnaire after nerve block (CS) and again at 48 hours
- Six minute walk test (CS) after the block
- Weight after the procedure.

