  - The subject will be asked to hold the morning diuretic medication and the morning dose will be given 3 hours after the procedure (CS). This is not expected to provide any risk to the stable chronic heart failure subject, especially since the diuretic medication will be resumed after completion of study that same day.
- Other medications can be continued, unless otherwise specified in the exclusion criteria.

Procedure:

1. Subjects will undergo elective right heart catheterization in the Duke catheterization laboratory lab as ordered by the primary team. A

cardiopulmonary exercise test will be added if not already ordered by the primary provider. Central hemodynamics will be recorded (baseline, prior to nerve block) (SOC). The access site for the right heart catheterization will be radial, brachial or cervical (SOC) to allow a prone positioning of the subject for the splanchnic nerve block described in the next paragraph. Additional baseline RHC numbers will be recorded with legs elevated, which is done to simulate a fluid bolus.

If the subject's hemodynamics provide any other concern for complications related to the splanchnic nerve block (such as underfilling or severe pulmonary hypertension, not related to left heart failure) as determined by the study personnel, the splanchnic nerve block and associated monitoring will not be performed. The subject will be considered a screen failure. Any information and samples collected prior to this will be discarded/destroyed per institutional policies.

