Before cardiopulmonary exercise begins, the subject will perform the Valsalva maneuver. The subject will sit up on the catheterization lab table, after the intravenous lines have been placed. The subject will have an empty syringe placed in their mouth. He/she will blow into the syringe for 30 seconds. This is the standardized method for performing the Valsalva maneuver (Saxena, M, Journal of American Heart Association, 2018). The intracardiac pressures will be measured continuously during the 30 seconds. Following the Valsalva maneuver, the subject will be placed supine on the stationary bike for cardiopulmonary exercise. Cardiopulmonary exercise testing will include a 20 W initial steady phase during which RHC numbers will be recorded and echocardiogram with liver blood flow will be obtained. This will take up to 7 minutes followed by quick (every 1 minute increase in 20W) ramp to peak exercise. At peak exercise repeat hemodynamics and echocardiography will be obtained.

Subjects will further be monitored with:

[figure not shown]
- Telemetry (SOC)
- ClearSite/CheetahMedical/Sphygmocor/ReDS for continuous non-invasive hemodynamic/lung fluid content recording (CS)
- Continuous urine output (ml/hour) recording if foley is present (SOC)
- A non-invasive wrist monitor/chest band to monitor the heart rate variability

Baseline hemodynamics and exercise CPX will be performed before and after the nerve block detailed below.

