2. Unilateral splanchnic nerve block performed by an anesthesiologist (see images below) (CS). The anesthesiologist will perform a unilateral block to the splanchnic nerve. The blood pressure will be checked, after 15 minutes, post-block. If the systolic blood pressure is reduced by  $> 20$ mmHg, the contralateral splanchnic nerve will not be blocked. Following the right heart catheterization procedure the subject will be prone on the abdomen. Central venous access remains in place. Needle will be placed under fluoroscopic guidance in the posterior chest wall. Anesthetic solution (1.5% lidocaine with 1:200,000 epinephrine and of 0.5% ropivacaine) will be injected. Lidocaine 1.5% with Epinephrine 1:200,000 will be used initially to confirm extravascular administration. The subject will then be placed back on his/her back. The subject will then undergo repeat hemodynamic measurement with the RHC catheter that was already in place. Then the subject proceeds with invasive cardiopulmonary testing after a 30 minute break. The central venous catheter will be removed after the hemodynamic monitoring/testing is completed in the catheterization laboratory.

Additional measurements include:

- Orthostatic vitals (CS).
- Dyspnea questionnaire (CS)
- Echocardiography and liver flow measurements (CS)

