#### Blood samples processing:

Some blood samples collected before and after the nerve block (plasma metanephrines, plasma catecholamines, angiotensin II and arginine vasopressin, lactate) will be processed (centrifuged) and stored at -70 degrees Fahrenheit before sent out to an external lab. Storage

duration may vary between weeks to months. Samples will be stored in a research freezer located on the 7th floor of Duke North (cath lab research freezer). As part of the study, we will send blood for study-related laboratory tests to the Mayo clinic and Inter Science Institute. These would include laboratory tests such as metanephrines, vasopressin, catecholamines, and angiotensin. A data transfer agreement is already in place.

Safety endpoints:

- The duration of the anesthetic block is estimated for 12-24 hours. The subject will be monitored for up to 3 hours in the catheterization laboratory/holding area, if there is any concern or evidence of procedure related complications the will be kept overnight in the cath lab holding area. A potentially observed effect of the block to prevent discharge the day of procedure could be orthostatic hypotension. will also be contacted at 48 hours post procedure to ascertain any potentially missed complications. Further the subject's medical chart will be observed for 6 months following study enrollment to evaluate for admissions for heart failure.

Incidence of major side effects has been reported to be <1:1000 and are expected to occur immediately post nerve block. They include:

- Pneumothorax, possibly requiring a chest tube
- Aortic puncture with retroperitoneal bleed or hemothorax
- Spinal cord trauma with possibly paralysis

Incidence of minor side effects like:

- Orthostatic hypotension
- Pain at puncture site and intercostal neuralgia
- Gastrointestinal dysmotility including diarrhea, constipation and abdominal cramping
- Bleeding at puncture site

Efficacy endpoints:

The following efficacy endpoints will be evaluated:

- Primary:
- Improvement in 20 W and peak exercise PA mean and wedge pressure
  - Reduction in central venous pressure and/or pulmonary artery pressure (diastolic) and/or pulmonary capillary wedge pressure at 30 minutes after nerve block

Secondary:

- Reduction in central venous pressure and/or pulmonary artery pressure (diastolic) and/or pulmonary capillary wedge pressure at 30 minutes after nerve block

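### The held diuretic is given unconditionally, at or after the end of post-block observation on the likeliest reading, and no orthostatic reading is tied to the dose

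*Combined protocol and SAP*

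**What the plan says.** Section 4, Follow up procedures, sets the observation period for the "lidocaine splanchnic nerve block the will be observed for monitored in the cath lab holding area for 3 hours following nerve block (SOC"). The Safety endpoints text words it as a maximum: "The subject will be monitored for up to 3 hours in the catheterization laboratory/holding area". An overnight stay is available if staff suspect or find a complication.

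The same text gives the expected length of the block: "The duration of the anesthetic block is estimated for 12-24 hours". It also names the relevant side effect: "A potentially observed effect of the block to prevent discharge the day of procedure could be orthostatic hypotension".

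For subjects on diuretics, the pre-procedure part of section 4 has the morning dose held, and then "the morning dose will be given 3 hours after the procedure (CS"). It does not say whether the procedure is the block or the whole cath lab session, where the dose is taken, or what would lead staff to withhold it. The stated reason for moving the dose is to keep it from disturbing the intervention.

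Orthostatic vitals are planned before the procedure and again afterwards: in step 2 of the Procedure text, in Follow up procedures, and in the Recovery column of the study events table. None of the later entries has a clock time. After discharge the scheduled contacts are phone calls at 24 h, 48 h and six months.

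**The concern.** The block enlarges splanchnic venous storage, and section 3 describes transient orthostatic hypotension as its most common side effect, usually prevented by giving fluid beforehand. A diuretic works in the opposite direction. The schedule gives it while the block is expected to be active, around or after the time monitoring stops, with no condition on the subject's standing blood pressure.

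At stake is whether the site sees the subject's postural response before adding a second volume-lowering step, and whether it sees the combined effect at all. Followed as written, the plan lets a subject take the diuretic with no later blood pressure check and no scheduled contact before the 24 h call. This is a matter of subject safety and of complete adverse-event data. The hemodynamic endpoints and the sample size are not affected.

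**Working it through.** The plan gives no figure to reproduce. The check is a timeline, with time 0 at completion of the block.

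Inputs:
- Observation ends at 3.0 h (Follow up procedures), or at 3 h at most (Safety endpoints).
- The diuretic is due 3 h after the procedure (section 4, pre-procedure list).
- The block lasts 12-24 h (Safety endpoints).
- Cath lab time after the block includes a break: "Then the subject proceeds with invasive cardiopulmonary testing after a 30 minute break". The exercise test then starts with a 20 W stage: "This will take up to 7 minutes followed by quick (every 1 minute increase in 20W) ramp to peak exercise". The length of the ramp is not given.
- The first later contact is the call at 24 h (Phone Call).

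With observation counted from the block:

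| | Procedure = block | Procedure = cath lab session, break only | Cath lab session, break plus full 7 min at 20 W |
|---|---|---|---|
| Dose time | 0 + 3 = 3.0 h | 0.5 + 3 = 3.5 h | 37/60 + 3 = 3.62 h |
| After observation ends | 0 min | 30 min | 37 min |
| Left of a 12 h block | 12 - 3 = 9 h | 12 - 3.5 = 8.5 h | 12 - 3.62 = 8.38 h |
| Left of a 24 h block | 24 - 3 = 21 h | 24 - 3.5 = 20.5 h | 24 - 3.62 = 20.38 h |
| Until the 24 h call | 24 - 3 = 21 h | 24 - 3.5 = 20.5 h | 24 - 3.62 = 20.38 h |

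The last two columns are partial counts. They leave out the ramp, the repeat resting hemodynamics, the post-block Valsalva and repositioning. Thirty minutes is therefore a minimum under that reading, and 37 minutes is not an upper limit. The hours of block remaining in those two columns are correspondingly slight overstatements.

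Time 0 is itself loose. The second side is blocked only after a 15-minute blood pressure check, and may not be blocked at all. The plan does not say which injection starts the clock.

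Orthostatic readings tied to the dose: none. The recovery set could by chance be taken after the dose, but nothing schedules it there. The study events table has no orthostatic entry at 24 h, 48 h or six months.

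**The case against.** The strongest reply is that the plan already has several layers of protection. Subjects need a systolic pressure above 100 mmHg and elevated filling pressures, and the block is not done if the subject is underfilled. After the block there are recovery orthostatic vitals, a second exercise test and a walk test. An overnight stay is available, and orthostatic hypotension is named in connection with it. Section 12 classes the effect as mild and time limited. Calls follow at 24 h and 48 h, the latter described this way: "will also be contacted at 48 hours post procedure to ascertain any potentially missed complications". Section 15 lists hypotension among the effects to be recorded. The late dose is deliberate, and section 4 states that no risk is expected from it in a stable subject.

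Much of this stands, and it limits the point. But the no-risk statement concerns holding and resuming the diuretic; it does not discuss dosing under an active block. The overnight stay depends on a visible problem, and an untimed reading taken before the dose cannot show the combined effect. The calls measure no blood pressure.

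The wording also allows a milder timeline. If the 3 h of observation were counted from the end of cath lab testing, the dose would fall at the end of observation or inside it. The phrase that counts from the nerve block, and the combined cath lab and holding-area limit, favor the reading used above, but this is ambiguity. Under any reading, no orthostatic check is tied to the dose.

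A reader might also infer that the present schedule contaminates the urine output and renal endpoints with diuretic effect. The documents do not support that as a defect. The dose is placed late to avoid it, and samples taken before the subject leaves would normally precede it. The issue arises mainly if subjects are kept after dosing.

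**Conclusion.** The point holds as a gap in scheduling and dosing rules. The diuretic is given unconditionally at the end of observation if the procedure means the block, or at least about 30 minutes after it if the procedure means the cath lab session and observation runs from the block. Roughly 8-21 h of block would remain, with no orthostatic reading linked to the dose. This assumes the protocol's own estimate of block duration and observation of the full 3 h.

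A reader might go further and infer that subjects face a demonstrated risk of postural collapse at home. The documents do not show this. They give no rate of postural hypotension after discharge, do not state how many of the up to 30 subjects take a diuretic, and do not say that the dose is taken at home. The figures describe timing, not risk. The change is still recommended, because the protocol itself links the effect to discharge and making the dose conditional costs very little.

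**What to change.** In section 4 (pre-procedure diuretic instructions and Follow up procedures):

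1. Define the dose time relative to the block, stating which injection starts the clock.
2. Take the already planned recovery orthostatic vitals at the end of observation, just before the dose, and compare them with the pre-procedure set.
3. Give the diuretic only if there is no symptomatic or clinically relevant new postural fall. Otherwise hold it and use the overnight stay. The investigator should set any numeric limit; the 20 mmHg rule for the second side of the block is a different measurement and should not be borrowed.
4. If the dose is given on site, repeat the orthostatic vitals before the subject leaves, after a wait set by the investigator. Take the final urine output and labs before the dose, so that the wait does not bring diuretic effect into those endpoints.

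Asking about orthostatic symptoms, syncope and falls at the 24 h and 48 h calls is an optional addition to the wording.

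Cost: steps 1 to 3 reorder existing work. Step 4 adds one orthostatic set, 5 + 5 + 5 = 15 minutes (reading the 1+5 notation as measurements at 1 and 5 minutes). If all 30 subjects took a diuretic this would be 30 x 15 = 450 minutes, or 7.5 h. The wait comes on top and may be the larger burden. The documents give no diuretic route or onset from which to size it, and they do not show how long is needed to capture the combined effect. A few more overnight stays are possible.

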### **2. Purpose of the Study:**

Splanchnic vasoconstriction may contribute to decompensation of chronic heart failure via volume redistribution from the splanchnic vascular bed to the central compartment. This is a sympathetically mediated reflex and can be interrupted through a splanchnic nerve block. Therefore, we hypothesize that interruption of the efferent/afferent innervation of the splanchnic vasculature will decrease cardiac congestion and improve renal function in subjects presenting with heart failure.

Objectives:

1. We will determine if splanchnic nerve blockade decreases cardiac preload as measured by invasive hemodynamics.
2. We will determine if splanchnic nerve blockade will improve invasive hemodynamics during exercise.
3. We will determine if splanchnic nerve blockade improves symptoms of shortness of breath.

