#### **4. Design & Procedures:**

This study will be a prospective, uncontrolled clinical trial. The study will not be controlled as invasive monitoring of hemodynamics will be performed, allowing clear demonstration of a cause-effect relationship.

This study aims to piggy-back on an elective right heart catheterization (RHC) in subjects with chronic heart failure. The right heart catheterization will be part of the subject's standard of clinical care (SOC). Subjects eligible for this study will be referred to the Duke cath lab for the evaluation of cardiac filling pressures because it is found to be necessary by the outpatient provider. This will occur in the cardiac catheterization lab. Subjects get scheduled for RHC days to weeks (2-3) ahead of their procedure. The eligible subject will be contacted before the study to be informed about the eligibility for the study and basic information about the study will be provided over the phone shortly after they have been scheduled. Subject will be consented in person in the morning of the procedure.

The subject will undergo pre procedural testing as demonstrated below in the flow chart (all part of the clinical study - CS). Besides the RHC (SOC) the subject will undergo an invasive cardiopulmonary exercise with the RHC in place. Baseline evaluation is followed by a regional nerve block (bilateral splanchnic nerves) while the subject is in the catheterization lab. This will be performed by an anesthesiologist experienced in splanchnic nerve blocks.

Figure 2: Study flow chart

[figure not shown]

Table: Study events

Required Assessment	Pre procedure (day of)	Baseline (intra-procedure)	Block	Post Block Procedure	Recovery	24 h after procedure	48 h after procedure	6 Months after Procedure (±14 days)
Vitals (BP, HR, RR, SpO2)	X (SOC)	X (SOC)	X (SOC)	X (SOC)	X (SOC)			
Weight	X (SOC)				X (SOC)			
Orthostatic vitals	X (CS)				X (CS)			
Urine output (continuous recording)	X (CS)	X (CS)	X (CS)	X (CS)	X (CS)			
Valsalva		X (CS)		X (CS)				
Labs: BMP, pro-BNP, urine sodium,	X (SOC/CS)				X (CS)			
Labs (Angiotensin II), Plasma Metanephrines, Vasopressin, Plasma Catecholamines, Lactate		X (CS)		X (CS)				
Dyspnea Questionnaire		X (CS)		X (CS)	X (CS)	X (CS)	X (CS)	
Six minute walk test	X (CS)				X (CS)			
Impedance and lung fluid content measurement		X (CS)		X (CS)				
Heart rate variability	X (CS)	X (CS)	X (CS)	X (CS)	X (CS)			
Echocardiogram		X (CS)		X (CS)				
Invasive CPX		X (SOC/CS)		X (CS)				

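### Epinephrine is injected between the two catecholamine draws, so a rise or the absence of a fall in measured epinephrine cannot be read as an autonomic effect of the block

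*Combined protocol and SAP*

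**What the plan says.** **Injection.** Section 4, Procedure step 2: "Anesthetic solution (1.5% lidocaine with 1:200,000 epinephrine and of 0.5% ropivacaine) will be injected". It adds: "Lidocaine 1.5% with Epinephrine 1:200,000 will be used initially to confirm extravascular administration". No volume is given. One side is blocked first. If systolic pressure has dropped by more than 20 mmHg at the 15-minute check, "the contralateral splanchnic nerve will not be blocked".

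**Draws.** The Study events table has a row, "Labs (Angiotensin II), Plasma Metanephrines, Vasopressin, Plasma Catecholamines, Lactate", marked in the intra-procedure baseline column and the post-block column. Follow up procedures says that "plasma metanephrines (if on inotropes), plasma catecholamines, vasopressin, lactate, and urine sodium will be collected immediately before and after the procedure". Blood samples processing describes these samples as taken before and after the block. The Pre-procedure list also names angiotensin II, vasopressin and catecholamines.

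**Use.** Under Exploratory aims, the change in cardiac and autonomic markers after the block is of interest, with angiotensin and catecholamines named. Section 14 compares baseline with post-intervention by paired t-test at the two-sided 5% level.

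**Design.** "This study will be a prospective, uncontrolled clinical trial". Section 2 describes the mechanism: "This is a sympathetically mediated reflex and can be interrupted through a splanchnic nerve block".

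**The concern.** The aim treats plasma catecholamines as a readout of the subject's own sympathetic activity. One of the catecholamines is also given as a drug between the two measurements. Section 2 makes a fall the natural direction of interest, although the aim itself names none. Injected drug works against seeing a fall and could produce a rise that is mistaken for sympathetic activation.

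Section 4 justifies the lack of controls by the invasive haemodynamic monitoring. That argument does not extend to a plasma assay of a substance that has just been injected. No readable passage mentions the injected epinephrine as a source of the measured level, sets an interval between injection and second draw, or separates epinephrine from norepinephrine.

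A second, smaller matter is the timing of the draws relative to exercise, which bears on catecholamines and lactate alike.

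**Working it through.** The plan gives no figure on this point, so there is nothing to reproduce. The check is the order of events, the sign of the bias, one conversion, and a comparison of the timing passages.

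**1. Order of events.** The table, Follow up procedures (if procedure there means the block) and Blood samples processing all put one draw before the block and one after. The epinephrine-containing solution is used at the start of the block. The drug therefore falls between the draws.

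**2. Sign of the bias.** For each subject write

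D = A + E + O,

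where D is the measured change in epinephrine, A is the autonomic effect of the block, E is injected epinephrine still present at the second draw, and O is everything else between the draws (first exercise test, prone positioning, needling). E cannot be negative. The paired t-test examines the mean of D, not of A.

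- Mean D at or above zero: compatible with a negative A offset by E, with A = 0, or with a positive A. It is not interpretable as an autonomic effect.
- Mean D below zero: E cannot by itself be the cause. O still can, so a fall is not clean evidence either.

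The same holds for metanephrine and for any total that includes either fraction. The documents name no fractions. The solution lists no norepinephrine, so this direct contribution does not apply to norepinephrine or normetanephrine.

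**3. Amount injected.** 1:200,000 means 1 g in 200,000 mL: 1,000,000 micrograms / 200,000 mL = 5 micrograms/mL. Volume is not stated. At assumed volumes of 1, 3, 5 and 10 mL the amount is 5, 15, 25 and 50 micrograms. These are amounts injected, not amounts in plasma at the second draw. That would also need absorption, clearance and the injection-to-draw time, none of which is given. No shift in SD units, and so no probability of a misleading test result, can be derived.

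**4. Draws and exercise.**

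| Place | What it says about these draws |
|---|---|
| Study events table | Baseline (intra-procedure) and post-block columns; exercise testing is marked in the same two columns |
| Pre-procedure list | Catecholamines listed, though the table has no pre-procedure mark for them |
| Follow up procedures | Immediately before and after the procedure; metanephrines only if on inotropes |
| Blood samples processing | Before and after the block |
| Procedure steps 1 and 2 | An exercise test to peak before the block; after it, "Then the subject proceeds with invasive cardiopulmonary testing after a 30 minute break" |

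None of these orders a draw against the exercise test of its phase. If procedure means the block and immediately is taken literally, the first draw could follow the first exercise test and the second precede the second test. That is one possible reading, not an established sequence. The table does not carry the inotrope condition on metanephrines.

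**The case against.** The strongest reply is about weight. One fraction of one marker group in an exploratory aim is touched, and the aim states no direction and makes no claim. Use of the solution to confirm extravascular placement fits a small check dose, and little may remain at the second draw. All of that stands. It limits the importance of the point without removing it, because the volume and timing that would show the effect to be trivial are not in the readable text.

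Three stronger readings are tempting and are not supported:

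- **That the draw times contradict one another.** The table, Follow up procedures and Blood samples processing agree if procedure means the block. The Pre-procedure list also contains the post-block echocardiogram, so it is not a strict timing list. Figure 2 is not shown and may place the draws. A rest/exercise mismatch is not excluded, but neither is it demonstrated.
- **That the epinephrine dose depends on the blood pressure response.** The second side may be omitted, but the text does not say that the epinephrine solution is used again on that side. Response-dependent exposure is only a possibility.
- **That the exposure could never be examined afterwards.** The readable text does not ask for volume, sides or injection-to-draw time. Procedure images are not shown, however, and procedural records may hold these items.

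It is also fair to say that norepinephrine does not give clean attribution, since exercise, positioning and needling remain between the draws. A second draw before exercise may also lie nearer the injection than one after it, which is a further reason to keep epinephrine descriptive.

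**Conclusion.** The point holds. As written, the plan would test a change in catecholamines across an injection that contains one of them, without controls. A rise, or no fall, in epinephrine, metanephrine or a total including them cannot be read as an autonomic effect. The direction follows from the order of events and from E being zero or positive.

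The size cannot be derived from the documents and may be negligible. A reader might infer that the study's main results are compromised. They are not affected by this point: the primary and secondary endpoints do not use these samples. The timing matter is secondary and depends on what Figure 2 shows.

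The reason to act is that the remedy is cheap, while unrecorded times and mistimed samples may not be recoverable later.

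**What to change.** - **Exploratory aims and Section 14:** name norepinephrine (normetanephrine where metanephrines are run) as the catecholamine for the exploratory paired test. Report epinephrine and metanephrine descriptively, with the injected epinephrine acknowledged.
- **Study events table, Pre-procedure list and Follow up procedures:** reconcile them so that both draws are at rest before the exercise test of the same phase. State in one place who has metanephrines measured.
- **Data collection:** record for each subject the volume of epinephrine-containing solution, the sides injected and the time from injection to the second draw. Note inotrope use when interpreting the results, since the inclusion criteria admit subjects on inotropes.

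**Cost.** Wording, draw timing and three data items, with no extra tubes or procedures. The laboratory must report fractions, which the documents do not confirm. Epinephrine is lost as an inferential marker. The norepinephrine change stays exploratory and is not solely attributable to the block. No change to the injected solution or to the block is proposed.
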